8. STUDY DRUG ADMINISTRATION/ASSIGNMENT

8.1 Study Drug

The study drugs include ondansetron and placebo. Neither of these drugs are investigational. The University of Rochester Investigational Drug Service will supply, package and label the study drugs. Each 8 mg ondansetron tablet contains ondansetron hydrochloride dehydrate equivalent to 8 mg of ondansetron. Each tablet also contains inactive ingredients lactose, microcrystalline cellulose, pregelatinized starch, hypromellose, magnesium stearate, titanium dioxide, triacetin, and iron oxide yellow¹⁰.

8.2 Dosage of Study Drug

The dosage of ondansetron will be 8 mg, orally, once.

8.3 Subject Enrollment/Randomization

Subjects will be randomized to receive either ondansetron or placebo. They will be assigned via simple random allocation through the use of a computer software program that generates a random sequence.

8.4 Accountability of Investigational Supplies

The University of Rochester Pharmacy pharmacist will be responsible for receipt, storage, dispensing, collection, accountability and disposal of the investigational

drug. This includes maintaining accurate records of drugs received, used and returned. The pharmacist is the unblinded third party.

8.5 Subject Withdrawal of Study Drug

Subjects may stop study drug and still continue to be followed in the study.

8.6 Emergency Drug Disclosure

Drug disclosures will be maintained via envelopes. The Study Coordinator will receive and maintain this information. Disclosure of the subject's envelope should occur only in the case of a medical emergency. If such action is necessary, the pharmacist will reveal whether the subject received ondansetron or placebo, and this in turn will be revealed to the subject. Subjects will not be withdrawn from the study should drug disclosure occur.

9. SAFETY AND REPORTABLE EVENTS

9.1 Adverse Event Definition

An adverse event is any symptom, sign, illness, or experience which develops or worsens during the course of the study, whether or not the event is considered related to the study survey.

9.2 Serious Adverse Event

A serious adverse event is defined as any adverse medical experience that results in any of the following outcomes:

- death;
- is life-threatening;
- requires inpatient hospitalization or prolongation of existing hospitalization;
- results in persistent or significant disability/incapacity;
- is a congenital anomaly/birth defect; or
- requires medical or surgical intervention to prevent permanent impairment or damage.

9.3 Recording Adverse Events

At each subject visit the site study staff will assess adverse events by recording all voluntary complaints of the subject and by assessment of clinical and laboratory features. At each study visit, the subject should be questioned directly regarding the occurrence of any adverse experience since her last visit.

All adverse events, whether observed by the Investigator, elicited from or volunteered by the subject, should be documented. Each adverse event will include a brief description of the experience, the time of onset, the time of resolution, the duration and type of experience, the severity, the relationship to the study, contributing factors, and any action taken with respect to the study.

The recording of adverse events will take place from the time that the subject signs the consent until the subject completes the study (1-2 days after signing the consent) or withdraws from participation.

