5. METHODS AND STUDY PROCEDURES

Patients will be approached for participation in the randomized controlled trial after they have completed their pre-operative consultation and have already consented for pregnancy termination. Once patients are consented, they will be randomized to either the placebo or ondansetron group. The study medication will be taken 30 minutes prior to doxycycline medication the night prior to the pregnancy termination. Doxycycline prophylaxis is currently the standard of care, and is not part of the study procedure. Randomization scheme will be generated by computer generated random number blocks using a 1:1 ratio. Allocation will be done by sequentially numbered opaque sealed envelopes. The pharmacy will be compounding the study medication so that it looks exactly like the placebo tablet, in appearance, texture and smell. Once consented and randomized during their clinic visit 1-2 days before the procedure, patients will fill out a demographic questionnaire regarding their age, race, relationship status, income and education level, pregnancy history, gestational age, and symptoms of nausea and vomiting thus far in the pregnancy. This questionnaire will also include questions regarding cigarette and THC use, as well as any diagnoses of gastroesophageal reflux disease or hyperemesis gravidarum. They will then fill out a baseline visual analog scale rating their nausea, pain and anxiety, prior to leaving the office.

The study coordinator will also conduct a chart review for select information. For participants enrolled prior to this version date, it will be retrospectively collected. For participants after this protocol version date, it will be collected at the time of enrollment. They will collect Gestational Age at Procedure Date (weeks/days), Cervical Preparation (Mifepristone Y/N) (Misoprostol Y/N) (Cervical Dilators Y/N, IF Y, How Many?) Genetic Indication for Termination? (Y/N).

The patients will then be given a symptom/medication log to take home. The patients will use the log to record symptoms they experience from the time they take the ondansetron or placebo to the time that they present for their procedure. The log will include the timing of the study medication, doxycycline, whether the doxycycline was taken with food (and the time of/type of food if applicable), pain medications, and misoprostol. The log will also include the time of nausea and vomiting, and the severity of the nausea and pain (if applicable).

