When patients present to the hospital for their procedure, the study coordinator, [name], [name], or [name] will give them a second visual analog scale to fill out which asks them to rate their nausea, pain and anxiety. This scale will be identical to the one they filled out at their clinic visit. This scale will be filled out prior to their procedure. When the IV is placed for their procedure, a nurse will also draw a single 7 mL tube of blood; there are no additional needle sticks for this blood draw. The blood sample will later be tested for doxycycline serum levels.

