9.4 Responsibilities for Reporting Serious Adverse Events

All serious adverse experiences that occur during the study period will be recorded. The recording of experiences will occur from the time of signing of the consent until the subject completes the study or withdraws from participation.

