10.2 Potential Risks

Potential risks to subjects include the possibility of an adverse reaction to ondansetron (including headache, fatigue, malaise, constipation, drowsiness, sedation, dizziness, agitation, anxiety, paresthesia, sensation of cold, pruritus, skin rash, diarrhea, urinary retention, increased serum ALT, increased serum AST, hypoxia, and fever). Important or life-threatening side effects occurring in less than 1% of patients include abdominal pain, accommodation disturbance, atrial fibrillation, depression of ST segment on ECG, dyspnea, flushing, hepatic failure (when used with other hepatotoxic medications), hiccups, hypersensitivity reaction, hypokalemia, hypotension, liver enzyme disorder, mucosal tissue reaction, myocardial infarction, neuroleptic malignant syndrome, positive lymphocyte transformation test, prolonged Q-T interval on ECG (dose dependent), second-degree atrioventricular block, serotonin syndrome, Stevens-Johnson syndrome, supraventricular tachycardia, syncope, tachycardia, tonic-clonic seizures, torsades de pointes, transient blindness (lasted ≤ 48 hours), vascular occlusive events, ventricular premature contractions, ventricular tachycardia, and weakness¹⁰. There is also a potential risk of a patient's greater realization of the nausea and vomiting they are experiencing due to doxycycline. The use of doxycycline is already standard of care.

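### The end of adverse event recording is not tied to any event, and nothing is planned to collect adverse events during sedation or anaesthesia, surgery and recovery

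*Combined protocol and SAP*

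**What the plan says.** Section 9.3 runs adverse event recording from signed consent "until the subject completes the study (1-2 days after signing the consent"), or until withdrawal. Section 9.4 gives serious events the same window, "from the time of signing of the consent until the subject completes the study or withdraws from participation", with no extension. Neither section says what event or clock time counts as completing the study.

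Section 5 fixes the calendar: "Once consented and randomized during their clinic visit 1-2 days before the procedure". The tablet is taken the evening before the procedure. The home log covers the time from the tablet to arrival at the hospital. Of the second visual analog scale, Section 5 says: "This scale will be filled out prior to their procedure". The last study activity of any kind is one tube of blood, drawn when the IV is placed.

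Section 9.3 collects events by direct questioning and clinical assessment at each visit. It also asks for documentation of anything an investigator observes or a patient volunteers. The coordinator's chart review in Section 5 is limited to gestational age, cervical preparation and genetic indication. For newly enrolled participants it is done at enrolment.

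Section 10.1 rates the study as greater than minimal risk. Section 10.2 lists sedation and hypoxia among the possible reactions to ondansetron. In its under-1% group it lists hypotension and "prolonged Q-T interval on ECG (dose dependent"). Section 13.2 plans no analysis or listing of adverse events.

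**The concern.** The tablet is taken the night before a procedure under sedation or anaesthesia. Some of the reactions in Section 10.2, such as sedation, hypoxia, hypotension and Q-T prolongation, are ones that staff would look for in theatre and recovery. Yet the plan schedules no look at that period.

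The protocol's own rationale also reaches into it. Section 1.2 says that patients with nausea or vomiting before surgery are given general anaesthesia with intubation at this institution. It names cardiovascular impairment and pneumonia as risks of general anaesthesia, and expects less nausea and vomiting to mean fewer general anaesthetics and lower patient risk. If allocation can change the anaesthesia route, it can change what happens in theatre and recovery, for better or worse. As written, the trial could miss both a harm and the safety benefit it argues for.

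Serious events are cut off at the same point. One of the criteria in Section 9.2 is "requires inpatient hospitalization or prolongation of existing hospitalization", which can be met after the procedure as well as before it.

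**Working it through.** No sample-size or test formula bears on this point. The check is a timeline built from the plan's own schedule.

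**Step 1: the plan's figure.** Section 9.3 puts the end of recording at 1-2 days after consent. Section 5 puts consent 1-2 days before the procedure. Take consent as day 0:

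| Case | Procedure | Stated end of recording | Gap |
|---|---|---|---|
| Consent 1 day before | day 1 | day 1 | 1 − 1 = 0 days |
| Consent 2 days before | day 2 | day 2 | 2 − 2 = 0 days |

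The stated window is reproduced. Recording ends on the day of the procedure, so the calendar does not decide whether the procedure is inside the window.

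**Step 2: order of events around the procedure.**

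1. Tablet, then doxycycline 30 minutes later, the night before (Section 5).
2. Arrival at the hospital: log closed and handed in, patient asked about taking the tablet (Sections 5 and 5.2).
3. Second visual analog scale, before the procedure (Section 5).
4. IV placed and study blood tube drawn (Section 5).
5. Sedation or anaesthesia, surgery, recovery, discharge: no study activity described.

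Items 2 to 4 all precede item 5. The number of study assessments scheduled from the start of sedation or anaesthesia onward is zero.

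**Step 3: could another provision fill item 5?**

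- *Questioning at visits (9.3).* Two patient contacts are described, the clinic visit and presentation for the procedure. The second is the only scheduled safety question after the tablet.
- *Chart review (5).* Its list contains no procedure or recovery events, and for new participants it is done before the procedure takes place.
- *Investigator observation (9.3).* This could catch an event in item 5, but only if an investigator is present and takes the window to be still open.
- *Event details (9.3).* Each event needs a resolution time and a duration. For an event still present on arrival, no later contact is planned at which these could be completed.

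No provision gives systematic collection in item 5.

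**Step 4: how many patients.** The gap applies to every patient who goes on to the procedure. Planned enrolment is 150 per arm in Section 13.1 and 160 per arm in Section 3.1.1. The evaluable target is 122 per arm (Section 13.1). The documents give no rate of events in theatre or recovery, so the number of events missed cannot be estimated.

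**The case against.** A reader might infer that recording is set to stop before the procedure, so that events in theatre and recovery must go unrecorded. The documents do not support that. Completion is undefined and its only gloss is a day count that falls on the procedure day, so a calendar-day reading takes in same-day surgery and recovery. Section 9.3 requires events seen by an investigator to be documented, and Section 4.1 says the investigators offering participation are caring for these patients anyway. What remains is that collection would depend on who is present and how that person reads an undefined term. That is not systematic collection.

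The listed harms should also not be overstated. Hypotension and Q-T prolongation are in the under-1% group. At 150 per arm, that means fewer than 150 × 0.01 = 1.5 expected cases of each in the ondansetron arm (1.6 at 160), over any window. A longer window will not yield a useful formal comparison of such rare events. The documents also do not say how long one tablet acts, so they do not show that any listed effect would appear the next day. Both points stand. They argue for a simple listing rather than a test. They do not justify leaving the period unobserved, since sedation and hypoxia are listed outside the under-1% group and the anaesthesia-route argument in Section 1.2 does not depend on duration of action.

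Two further inferences should be resisted. One is that a planned safety comparison would be falsely reassuring: Section 13.2 plans none. The other is that the hospitalisation criteria would be met chiefly after the procedure: no figure in the documents supports this.

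**Conclusion.** The point holds as a gap in systematic collection. The window ends on the procedure day at an unspecified moment, every described study activity precedes the procedure, and no event assessment is scheduled from sedation or anaesthesia to discharge. This applies to every patient who goes on to the procedure, in both arms.

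The conclusion rests on two readings: that Sections 5 and 9 describe all study contacts, and that Section 9.3's visits are the clinic visit and presentation for the procedure. Nothing in the documents points to a further contact.

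It affects safety information only. The primary outcome is measured before the procedure, and neither it nor the sample size changes. This is a worthwhile, inexpensive improvement and not a flaw that undermines the trial.

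**What to change.** 1. In Sections 9.3 and 9.4, define the end of adverse event and serious adverse event recording as discharge after the procedure, for every patient who took the study tablet and has not withdrawn consent to data collection. This wording also keeps in view patients who took the tablet but are withdrawn under Section 7 for not taking doxycycline.
2. In Section 5, add procedure and recovery events to the coordinator's chart review. Date that part of the review to the procedure day, since the present review is done at enrolment.
3. In Section 13.2, add a descriptive listing of adverse events by arm, separately before and after the start of the procedure. No test is needed.

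Cost: short edits to four sections and a somewhat wider chart review, using the routine record of the procedure and recovery. No visit, blood draw or change in treatment is needed. The downside is that procedural events unrelated to the tablet will also be captured. They will be captured in both blinded, randomised arms, and splitting the listing at the start of the procedure keeps them apart from the earlier events.

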9.4 Responsibilities for Reporting Serious Adverse Events

All serious adverse experiences that occur during the study period will be recorded. The recording of experiences will occur from the time of signing of the consent until the subject completes the study or withdraws from participation.

10. RISK/BENEFIT ASSESSMENT

10.1 Risk Category: Greater than minimal risk.

10.2 Potential Risks

Potential risks to subjects include the possibility of an adverse reaction to ondansetron (including headache, fatigue, malaise, constipation, drowsiness, sedation, dizziness, agitation, anxiety, paresthesia, sensation of cold, pruritus, skin rash, diarrhea, urinary retention, increased serum ALT, increased serum AST, hypoxia, and fever). Important or life-threatening side effects occurring in less than 1% of patients include abdominal pain, accommodation disturbance, atrial fibrillation, depression of ST segment on ECG, dyspnea, flushing, hepatic failure (when used with other hepatotoxic medications), hiccups, hypersensitivity reaction, hypokalemia, hypotension, liver enzyme disorder, mucosal tissue reaction, myocardial infarction, neuroleptic malignant syndrome, positive lymphocyte transformation test, prolonged Q-T interval on ECG (dose dependent), second-degree atrioventricular block, serotonin syndrome, Stevens-Johnson syndrome, supraventricular tachycardia, syncope, tachycardia, tonic-clonic seizures, torsades de pointes, transient blindness (lasted ≤ 48 hours), vascular occlusive events, ventricular premature contractions, ventricular tachycardia, and weakness¹⁰. There is also a potential risk of a patient's greater realization of the nausea and vomiting they are experiencing due to doxycycline. The use of doxycycline is already standard of care.

10.3 Protection Against Risks

The only additional risk may be loss of confidentiality. Study materials will be kept in a locked file cabinet.

10.4 Potential Benefits to Subjects

A potential benefit to subjects participating in this study is a decrease in their nausea and vomiting.

10.5 Alternatives to Participation

Patients who decline to participate in the study will receive the standard of care at our clinic for termination of pregnancy, which involves the use of doxycycline as a prophylactic antibiotic the night before the procedure, as well as misoprostol the morning of the procedure. They will also be able to take Ibuprofen or Tylenol #3 for pain. They will not fill out any surveys or logs or take the study drug.

11. CONFIDENTIALITY OF DATA AND INFORMATION STORAGE

11.1

Subject data will be identified in the research data set by random unique identifiable code.

The Study Coordinator will maintain the code to that information and it will be used to re-identify patients when they present for their procedure, in order to link together their demographic questionnaire, the two visual analog scales, their study medication, and the symptom/medication log. The research data will be secured in a locked filing cabinet during the study. No identifying information will be included in the research database except for the subject's ID number, any identifying information will be kept separately from the research database. Research files will be locked up when they are unsupervised, and only The Study Coordinator, [name], or [name] will be able to access the files.

12. RESEARCH INFORMATION IN MEDICAL RECORDS

No research data will be included in the subject's medical record.

13. DATA ANALYSIS AND MONITORING

13.1 Sample Size Determination

Based on Reeves' study as well as anecdotal data from our clinic population, we expect vomiting to occur in approximately 30% of our patients who take their doxycycline the night before their procedure. To have 80% power to detect a 50% decrease in nausea and vomiting, we will need 122 patients in each arm of the study. In order to account for subject withdrawal or non-compliance, we intend to enroll 150 patients in each arm of the study. This will be a total of 300 subjects.

13.2 Planned Statistical Analysis

Our primary outcome of vomiting, will be analyzed using chi-square analysis. All dichotomous outcomes will be analyzed using chi-square analysis. Continuous variables will be examined using t-tests. If demographic variables are found to be confounders with significance, they will be placed into a logistic regression model. SPSS software will be used for statistical analysis.

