1.2 Background

The use of prophylactic antibiotics are standard of care to prevent surgical site infections in gynecologic surgery¹. Doxycycline is the recommended antibiotic of choice for surgical pregnancy termination and completion of spontaneous abortion given its effectiveness, low cost, and rare occurrence of allergic reaction². Previous studies have shown that a common side effect of doxycycline is nausea and vomiting, with reported rates as high as 30-40%³. Nausea and vomiting may be reduced by taking the antibiotic with food⁴. Doxycycline given on an empty stomach the morning of a surgical pregnancy termination resulted in nausea and vomiting in 50% of patients and this rate was decreased to 15% when it was taken with food the night before surgery⁵. It is not known whether the use of scheduled prophylactic anti-emetics prior to doxycycline use would further reduce the rate of associated nausea and vomiting. The goal of our proposed study is to determine this.

Our study will be a double blinded randomized controlled trial that will examine whether the use of scheduled prophylactic anti-emetics prior to doxycycline use reduces the incidence of associated nausea and vomiting. Nausea and vomiting is distressing to patients and it affects their perioperative care. It is well documented that minor gynecologic procedures, such as uterine evacuations, can be performed safely with moderate and deep sedation without an endotracheal tube⁶. At our institution, patients experiencing nausea and vomiting prior to a surgical procedure receive

general anesthesia with endotracheal intubation, due to their symptoms, not because that would be the preferred route of anesthesia. For minor gynecologic procedures, the time for general anesthesia induction can be as long as the duration of the entire surgical procedure would be without general anesthesia. The use of general anesthesia increases the duration of time in the operating room, which increases the costs of operating room and anesthesia time, as well as recovery time for the patient⁷. General anesthesia also poses possible risks such as impairment of cardiovascular function and development of pneumonia^{8,9}.

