2. STUDY DESIGN

2.1 Overview

This will be a randomized controlled trial. Data will be collected by asking patients to fill out a demographic questionnaire and a baseline visual analog scale rating their nausea, pain and anxiety at their clinic appointment 1-2 days prior to their procedure. Patients will then take either ondansetron or a placebo 30 minutes prior to taking doxycycline the night before their procedure. They will then fill out a symptom/medication log recording their symptoms from the time that they take the study medication to the time that they present for their procedure. When they present for their procedure, patients will fill out a second identical visual analog scale rating nausea, pain and anxiety. The primary outcome is nausea and vomiting after taking the study drug and doxycycline the night prior to surgery. Doxycycline prophylaxis the night prior to surgery is the current standard of care. Eligible patients will be enrolled over the course of two years.

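### Section 13.2 lets significance tests on the trial data choose the supporting logistic model and states no use of the baseline VAS; a fixed model and ANCOVA would be better, while the primary chi-square stands (minor)

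*Combined protocol and SAP*

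**What the plan says.** Section 13.2 is the whole analysis plan. For the primary outcome it states: "Our primary outcome of vomiting, will be analyzed using chi-square analysis". The same test covers all dichotomous outcomes. For continuous measures it says "Continuous variables will be examined using t-tests", and for adjustment "If demographic variables are found to be confounders with significance, they will be placed into a logistic regression model". It does not say what is tested to identify a confounder (a difference between arms, an association with outcome, or both), at what threshold, or how the logistic result relates to the chi-square.

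The VAS is described outside 13.2. Section 5 has patients complete it at the clinic visit: "They will then fill out a baseline visual analog scale rating their nausea, pain and anxiety, prior to leaving the office". Section 2.1 adds the repeat measure: "When they present for their procedure, patients will fill out a second identical visual analog scale rating nausea, pain and anxiety". Section 13.2 mentions neither the VAS nor any use of its baseline value. The Section 5 questionnaire also records "symptoms of nausea and vomiting thus far in the pregnancy".

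**The concern.** Two choices in 13.2 give a weaker analysis than the collected data allow.

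**Selection by significance.** Allocation is random and 1:1 (Section 5), so a significant baseline difference reflects chance and does not identify a variable that predicts vomiting. A rule that waits for significance fixes no model in advance. Because it is limited to demographic variables, a literal reading also leaves out baseline nausea, a likely predictor that is already on file.

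**T-tests for a measure with a baseline.** The t-test sentence fits a comparison of follow-up scores, of change scores, or a paired test within arms. None of these is named. Both between-arm versions are, in large samples, at best as precise as ANCOVA with the baseline score as covariate.

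At stake are the quality of the supporting analysis and the precision of the VAS comparisons. The validity of the primary test and the sample size are not affected.

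**Working it through.** **Plan's own figure.** Inputs from 13.1: 30% versus 15% (a 50% decrease), 80% power, 122 per arm. Alpha is not stated; two-sided 5% is assumed. The pooled rate is (0.30 + 0.15)/2 = 0.225.

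n = [1.96 × √(2 × 0.225 × 0.775) + 0.842 × √(0.30 × 0.70 + 0.15 × 0.85)]² / 0.15² = 120.5, so 121 per arm.

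Power by the same formula is 80.5% at 122 and 87.9% at 150 per arm. The stated 122 reproduces.

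**How open the selection rule is.** If k independent items are tested for baseline difference at 5%, the chance of at least one significant result is 1 − 0.95^k. Section 5 lists 5 strictly demographic items (age, race, relationship status, income, education) and 12 questionnaire items in all. Hyperemesis is an exclusion in 3.2.2, which leaves 11. The chance is 23% for k = 5, 43% for k = 11 and 46% for k = 12.

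**What selection does to the primary comparison.** This was simulated with 122 per arm and 11 independent normal covariates, 2 of them prognostic at odds ratios of 1.5, 2 or 3 per SD. These covariate inputs are assumptions. There were 10,000 null runs per cell (30% in both arms) and 3,000 runs at 30% versus 15%. The ranges below run over the three odds ratios.

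| Reading of the rule | Model fitted (30% vs 15%) | Type I error after selection | Type I error if either result could be claimed | Chi-square and logistic disagree (30% vs 15%) |
|---|---|---|---|---|
| Baseline difference | 41–44% | 4.5–5.0% | 5.3–5.8% | 2.8–3.4% |
| Association with outcome | 94–100% | 4.6–5.1% | 6.5–7.4% | 5.5–12.8% |
| Both | 9–12% | 4.3–5.1% | 5.3–5.6% | 1.2–2.5% |
| Either criterion | 97–100% | 4.8–5.3% | 6.6–7.6% | 5.8–12.6% |

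The model-fitted column shows how far the wording is open. The next column shows that selection itself does little harm.

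**What a fixed model would give.** With one covariate at odds ratio 1, 1.5, 2 or 3 per SD and marginal rates of 30% and 15% (122 per arm, 20,000 runs), adjusted power is 80.5%, 81.4%, 83.3% and 87.1%. The chi-square gives 81.2%, 81.1%, 81.3% and 81.3%. Expected events are 122 × 0.30 + 122 × 0.15 = 54.9, enough for a model with three terms.

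**VAS.** Let r be the correlation between baseline and second score, with equal SDs; r is not in the documents. Relative to the follow-up t-test, the variance of the treatment contrast is 2(1 − r) for change and 1 − r² for ANCOVA. ANCOVA against change is therefore (1 − r²)/[2(1 − r)] = (1 + r)/2. Neither 1 − r² nor (1 + r)/2 exceeds 1.

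For an assumed 0.3 SD effect and 122 per arm, the follow-up test has expected z = 0.3/√(2/122) = 2.343 and power Φ(2.343 − 1.96) = 65%. Dividing 2.343 by the square root of each relative variance gives:

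| r | ANCOVA variance vs follow-up | ANCOVA variance vs change | Power: follow-up | Power: change | Power: ANCOVA |
|---|---|---|---|---|---|
| 0 | 1.00 | 0.50 | 65% | 38% | 65% |
| 0.3 | 0.91 | 0.65 | 65% | 51% | 69% |
| 0.5 | 0.75 | 0.75 | 65% | 65% | 77% |
| 0.7 | 0.51 | 0.85 | 65% | 86% | 91% |

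Simulation at 122 per arm agrees to within about one point.

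**The case against.** The strongest reply is that 13.2 already names the primary test. The logistic sentence comes later, is conditional, and nowhere says that it replaces the chi-square; the natural reading is a supporting analysis. That stands. A reader might infer that the primary result is left undecided or that its type I error is inflated. The documents do not support this: the 5.3% to 7.6% range needs permission to claim either result, which no section gives. In ordinary usage a confounder relates to both arm and outcome, and on that reading the two results disagree in only 1.2% to 2.5% of simulated trials.

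A reader might also infer that the plan discards the baseline VAS, or that the VAS tests carry an 8% to 9% error rate. Neither follows. A change-score t-test would use the baseline, so the most that can be said is that no use of it is stated. The error figure (8.3% at r = 0 to 9.4% at r = 0.7, if either the follow-up or the change test may be claimed) assumes a liberty that the plan does not grant, on a measure that it does not name as an outcome.

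Two further limits stand. Section 6 has misoprostol taken between the two scales, which may lower r; from r = 0 to 0.3, ANCOVA gains only 0 to 4 power points over the follow-up test. And the two-covariate model proposed below was not itself simulated, only a model with one covariate.

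Use of the baseline VAS can be questioned because it is completed after randomisation. It precedes study drug, and Section 1.2 says "Our study will be a double blinded randomized controlled trial", so it is a legitimate covariate. The exception is a late form: Section 7 lets the study coordinator help complete missing forms without a time limit, and Section 8.6 has the coordinator hold the disclosure envelopes. Section 5.2 expects completion in clinic, so few forms should be affected.

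**Conclusion.** The point holds as a minor one. The chi-square is named, valid and correctly sized, and selection leaves type I error at 4.3% to 5.3% under the assumed covariates. The weakness is that the supporting model is chosen by tests on the trial data from a list that, read literally, omits baseline nausea, when a better fixed model is available from data already collected.

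For the VAS, the large-sample advantage of ANCOVA over both between-arm t-tests does not depend on r; only its size does. Against the follow-up test it ranges from nothing at r = 0 to 26 power points (91% against 65%) at r = 0.7. Against change it ranges from 27 points (65% against 38%) down to 5 (91% against 86%). These figures rest on two-sided 5%, a 0.3 SD effect, 122 per arm and equal SDs, none of which except 122 is in the documents.

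**What to change.** Amend 13.2 as follows.

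1. Analyse each second VAS score (nausea, pain, anxiety) by ANCOVA on arm and the matching baseline VAS, as secondary outcomes. Use only baseline forms completed before study drug, and state a simple rule for missing baselines.
2. Replace the significance-based rule with one supporting logistic regression of the primary outcome, defined exactly as for the chi-square, on arm, baseline nausea VAS and nausea or vomiting so far in pregnancy (as coded on the questionnaire). Report it whatever the baseline balance.
3. For clarity, state that the chi-square alone decides the primary result.

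The cost is wording only: no new data, no change in sample size, and both models run in SPSS. Enrolment had already begun, since Section 5 says of the chart-review data: "For participants enrolled prior to this version date, it will be retrospectively collected". The amendment must therefore be dated before unblinding to count as pre-specified. There are two downsides. The adjusted odds ratio is a different quantity from the planned 50% decrease and should be labelled so. A few patients may also lack a usable baseline VAS.
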